9 ANALYSIS

9.1 Descriptive Information

Table 6 lists the summaries for patient disposition, analysis populations and protocol deviations.

Table 6. Clinical study RPL554-COV-201 analysis tables - Disposition.

Table #	Table Name	Table Contents
14.1.1	Patient Disposition.	The disposition of patients by treatment group and include study milestones total number screened, randomized, completed 7, 14, 29 days of treatment, completed Day 29 and Day 60 follow-ups and withdrawn patients in total and by withdrawal reason.
14.1.2	Screen Failures.	A summary of the reasons that patients were screened but not enrolled.
14.1.3	Major Protocol Deviations.	Major protocol deviations summarized by the reason for the deviation, the deviation category, treatment group, COVID disease severity and (separately) site for all patients.
14.1.4	Analysis Sets	The composition of analysis populations, including reasons for patient exclusion by treatment group.

Tables summarizing patient demographics are displayed in Table 7. Demographics include age/DOB, sex, height, weight, BMI (calculated), ethnicity, and race; smoking history, date of randomization and date of inhaler training.

Table 7. Clinical study RPL554-COV-201 analysis tables - Demographics.

Table #	Table Name	Table Contents
14.1.5	Baseline Demographic Characteristics.	Overall, by treatment group, by COVID disease severity and by baseline clinical status assessment using the 7-point ordinal scale for
		ITT, PP and SS (if different).

Summaries of baseline clinical characteristics are displayed in Table 8. Baseline clinical characteristics include brief physical exam findings, vital signs, clinical status assessment using the 7-point ordinal scale score, COVID-19 symptom onset, admission date, COVID disease severity, existing co-morbidities, surgical history, prior medications, concomitant medications, and COVID-19 standard medications and treatments.

pg. 21 Confidential

Table 8. Clinical study RPL554-COV-201 analysis tables - Baseline Clinical Characteristics.

Table #	Table Name	Table Contents
14.1.6	Baseline clinical characteristics (Eg. 7-point ordinal scale score, vital sign values, COVID disease severity, co-morbid conditions - obesity, hypertension, diabetes 1, asthma, and COPD).	Overall, by treatment group and COVID disease severity for ITT, PP and SS (if different).
14.1.7	Proportion patients with 7-point ordinal scale score or 3, 4 and 5, ITT.	Overall and by treatment group.
14.1.8	Proportion patients with COVID disease severity of mild, moderate, severe and critical, ITT.	Overall and by treatment group.
14.1.9	Disease onset (days with COVID symptoms, hospital admission date, COVID disease severity and oxygen need at randomization), ITT.	Overall and by treatment group.
14.1.10	Number and proportion taking concomitant dexamethasone or remdesivir, ITT.	Overall, by treatment group and COVID disease severity.
14.1.11	COVID-19 treatment and other respiratory medications introduced after randomization, ITT.	Overall, by treatment group and COVID disease severity.

9.2 Study Medication Compliance

Summaries of study non-medication compliance are listed in Table 9.

Table 9. Clinical study RPL554-COV-201 analysis tables - Study Medication Compliance.

Table #	Table Name	Table Contents
14.2.1	Study Medication Compliance	The number of patients with
	(number of patients who had study medication	discontinued or missed doses (except
	halted/slowed and the number of patients with	due to discharge) by treatment group
	missed doses)	for ITT and PP.
14.2.2	Patient study medication discontinuation by study day.	By treatment group for ITT and PP.

9.3 Primary Endpoint Analysis

The proportion of patients with recovery at Day 29 will be compared between treatment groups using a logistic regression model adjusting for treatment and COVID disease severity. The difference between treatment arms will be expressed as a difference in proportions as measured by the Cochran Mantel-Haenzel (stratum)-weighted estimator based on the fitted logistic regression model. The delta method will be used to calculate the standard error for the difference and the associated confidence interval [Ge, 2011]. In addition, the raw proportions per treatment group will be given. If 0 events in any of the groups only raw proportions will be given.

Sub-group analysis will only be performed for sub-groups with a minimum size.

Summaries of the results of the primary analysis are displayed in Table 10.

pg. 22 Confidential

Table 10. Clinical study RPL554-COV-201 analysis tables - Primary Analysis.

Table #	Table Name	Table Contents
14.2.3	Proportion of Patients with Recovery at 29	Overall and by Treatment Group
	Days, ITT	By Age Group
		By Gender
		 By COVID Disease Severity
		By Smoking History
		By # co-morbidities
14.2.4	Proportion of Patients with Recovery at 29 Days, PP	Overall and by Treatment Group

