6 INVESTIGATIONAL PLAN

6.1 Overall Study Design and Plan

The purpose of this study is to evaluate the effect of ensifentrine on the proportion of patients hospitalized with COVID-19 infection with recovery over 29 days.

This is a single center, randomized, double-blind, parallel group, placebo-controlled study to determine the efficacy and safety of ensifentrine 2 mg BID administered via pMDI added on to SoC treatment for COVID-19 infection compared to patients receiving SoC plus placebo.

Patients 18 to 80 years of age must be hospitalized with a confirmed diagnosis of SARS-CoV-2 infection confirmed by PCR test and displays at least one of the following: Respiratory rate greater than 24, new cough, new atypical chest pain, new dyspnea, oxygen saturation <97% at rest, chest x-ray with new changes consistent with COVID-19 related airspace disease.

Patients meeting criteria for inclusion and none of the criteria for exclusion at randomization will be randomized to receive study medication within 4 days of hospital admission until hospital discharge or up to 29 days of treatment, whichever comes first. Patients will be randomized 2:1 to receive one of the following study treatments:

- Treatment Arm 1 (n=30): Blinded ensifentrine (2 mg) pMDI BID + Standard of Care treatment for COVID-19 infection
- Treatment Arm 2 (n=15): Blinded placebo pMDI BID + Standard of Care treatment for COVID-19 infection

Randomized patients will receive blinded ensifentrine or placebo twice daily, approximately 12 hours apart in the morning and evening, through 29 days or until discharge from hospital, whichever is first. Patients will self-administer 4 actuations (puffs) pMDI observed by study staff at each dosing event.

During the treatment period, patients will undergo all assessments and procedures as outlined in the schedule of activities until hospital discharge. Patients completing treatment will complete a study contact (telephone or visit as required) within 4 to 10 days of discharge or early withdrawal. All enrolled patients will complete a telephone contact 26 to 32 days (Day 29) and 55-65 days (Day 60) following receipt of 1st dose of study medication for assessment of clinical status via the 7-point ordinal scale, need for re-hospitalization and vital status.

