	All-cause mortality at Days 29 and 60.	Clinical status assessed using the 7-point ordinal scale score.
		Death = 7-point ordinal scale score is equal to 7 or using a vital records search returns a death record, the date on the record will be the date of death.
	Proportion of patients alive and not in respiratory failure (invasive mechanical	Clinical status assessed using the 7-point ordinal scale score.
	ventilation or extracorporeal membrane oxygenation (ECMO)) at Days 7, 14 and 29.	The proportion of patients in each treatment arm that meet the definition of alive and not is respiratory failure.
		Alive and not in respiratory failure (invasive mechanical ventilation or ECMO) = 7-point ordinal scale score is equal to 1, 2, 3, 4 or 5.
	Proportion of patients needing re-hospitalization (post-dose Day 1 – Day 60).	Assessed following discharge: the eCRF question regarding re-hospitalization will be used at Day 29 and Day 60 follow-up contact.
		The proportion of patients in each treatment arm that meet the definition of re-hospitalization following discharge.
		Re-hospitalization = following their treatment with study medication and subsequent discharge from hospital, they were re-admitted to a hospital for COVID related issue(s).

pg. 15 Confidential

Endpoints		Definitions
	Total time of hospitalization	Clinical status assessed using the 7-point
	between Day 1 - Day 29 (measured in days).	ordinal scale score.
	(Hospitalized = # days where the 7-point ordinal scale score is equal to 3, 4, 5 or 6.
		Or 7-point ordinal scale score is equal
		to 7 if patient dies while hospitalized
		between Day 1-29.
	Change from baseline in 7-	Clinical status assessed using the 7-point
	point ordinal scale (Days 7, 14 and 29).	ordinal scale score.
		The mean change from baseline of the 7-point
		ordinal scale in each treatment arm as
	Total time on supplemental	assessed by the statistical analysis. Clinical status assessed using the 7-point
	oxygen (Day 1 - Day 29; measured in days).	ordinal scale score.
	. ,	Hospitalized patient supplemental oxygen = # days where the 7-point ordinal scale score is equal to 4, 5, or 6.
		 Or 7-point ordinal scale score is equal to 7 if patient dies while hospitalized between Day 1-29.
		Not hospitalized patient supplemental oxygen = # days where the 7-point ordinal scale score is equal to 2 (if required to have home oxygen).

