	Total time of non-invasive ventilation or high flow oxygen use (post-dose Day 1	Clinical status assessed using the 7-point ordinal scale score.
	- Day 29; measured in days).	Non-invasive ventilation or high flow oxygen use = # days where the 7-point ordinal scale score
		is equal to 5 or 6. • Or 7-point ordinal scale score is equal to 7 if patient dies while hospitalized between Day 1-29.
	Proportion of patients alive and with oxygen use at Days 7, 14 and 29	Clinical status assessed using the 7-point ordinal scale score.
	,	The proportion of patients in each treatment arm that meet the definition of requiring oxygen use.
		Hospitalized patient supplemental oxygen = the 7-point ordinal scale score is equal to 4, 5, or 6. • Or 7-point ordinal scale score is equal
		to 7 if patient dies while hospitalized between Day 1-29.
		Not hospitalized patient supplemental oxygen = the 7-point ordinal scale score is equal to 2 (if required to have home oxygen).
	Proportion of patients alive at Days 7, 14 and 29 with non-	Clinical status assessed using the 7-point ordinal scale score.

pg. 16 Confidential

Endpoints		Definitions
	invasive ventilation or high flow oxygen use	The proportion of patients in each treatment arm that meet the definition of requiring non-invasive ventilation/high-flow oxygen use.
		Non-invasive ventilation or high flow oxygen use = the 7-point ordinal scale score is equal to 5 or 6. • Or 7-point ordinal scale score is equal to 7 if patient dies while hospitalized between Day 1-29.
	Proportion of patients alive and receiving invasive mechanical ventilation or extracorporeal membrane oxygenation (ECMO) at Days 7, 14 and 29).	Clinical status assessed using the 7-point ordinal scale score. The proportion of patients in each treatment arm that meet the definition of requiring invasive mechanical ventilation.
		The 7-point ordinal scale score is equal to 6. • Or 7-point ordinal scale score is equal to 7 if patient dies while hospitalized between Day 1-29.
Safety Refer to Section 9, Table 12	Incidence of Adverse Events (AEs).	Number of AEs and number of patients with AEs for all TEAEs and for subcategories of AEs (SAEs, severe AEs, fatal AEs etc). Incidence = proportion of patients in each treatment arm that experience an adverse

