8.2 General Principles

This is a double-blind, placebo controlled randomized pilot study which may inform on treatment effect for future studies.

All analyses are considered exploratory and hypothesis-generating. All tests will be two-sided at 5% significance level. Hypothesis tested for the primary endpoint will be if addition of ensifentrine to SoC for up to 29 days could increase the proportion of patients with recovery versus standard of care plus placebo. The status according to the 7-point ordinal scale of all patients regardless of treatment withdrawal will be followed up during the scheduled treatment period (Day 29) and at a follow-up Day 60, or as far as possible.

Secondary endpoints are tested independently and there will be no adjustment for multiple tests.

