8.5 Missing Data

All attempts will be made to collect all data per protocol.

 The patients withdrawn from treatment will be followed up regarding their status according to the 7-point ordinal scale at Day 29 as far as possible (exceptions for patients with withdrawn consent or lost to follow-up) and this data will be the primary source for handling missing data in the study.

Any data point that appears to be erroneous or inexplicable based on clinical judgment will be investigated as a possible outlier.

• If data points are identified as outliers, sensitivity analyses may be performed to examine the impact of including or excluding the outliers. Any substantive differences in these analyses will be reported.

For survival analyses, patients with death as outcome will be censored at Day 29 (Day 60), unless the required event was reached prior to death. Patients who are lost to follow-up or terminate the study prior to Day 29 (Day 60) for other reason than death and prior to observing/experiencing the event will be censored at the time of their last observed assessment.

The only time to event analyses is the time to recovery.

For secondary endpoint analyses, the following imputation rules will be used for patients who are lost to follow-up, terminate early from the study, or do not have further outcome data available after discharge for any reason than death:

- Patients with no data collected at the actual time point of interest for other reason than
 death, the last assessment of their status prior to this time point will be used as a
 representative for that time point. Especially, if the patient's clinical status scale is 1 or 2
 at the last observed assessment, then the patient will be considered to be recovered
 through Day 29.
- For endpoints assessing total time (oxygen or non-invasive ventilator care), the status for patients with no data collected for other reason than death, will be assumed unchanged from last assessment of the score up to last day in the definition of the endpoint (Day 29). Thus, no extra days will be added for patients without oxygen or patients without non-invasive ventilator care at last assessment.
- Patients that die in the study will be handled as worst case in all the analyses, that is they are considered to be on oxygen need, non-invasive and invasive mechanical ventilator need for all time points following the death.

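### The SAP has no rule for an arm at 100%; the delta-method interval then ignores that arm's uncertainty and is usually too narrow, worst when placebo is 15/15

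*SAP*

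**What the plan says.** For the primary endpoint, recovery at Day 29, SAP 9.3 fits a logistic model with treatment and COVID severity and converts it to a stratum-weighted difference in proportions. On precision it states: "The delta method will be used to calculate the standard error for the difference and the associated confidence interval". Raw proportions are shown alongside. The one provision for a degenerate result is "If 0 events in any of the groups only raw proportions will be given".

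SAP 9.4.2 repeats the method and the rule for the secondary proportions. It also drops severity when events are few, which does nothing for an arm at 100%. It speaks of an event as something the patient fulfils, so for recovery zero events means that nobody in the arm recovered. Neither section covers an arm where every patient meets the endpoint, and no score, exact or penalised alternative is named.

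SAP 8.2 sets the standard for precision and the status of the results: "All tests will be two-sided at 5% significance level" and "All analyses are considered exploratory and hypothesis-generating".

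**The concern.** The sponsor provided for the boundary at 0% but not for the one at 100%, which a recovery endpoint is more likely to reach. Discharge on home oxygen counts as recovery, and patients needing mechanical ventilation at screening are excluded. Day 60 recovery and being alive without respiratory failure can sit nearer 100% still.

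When an arm is at 100%, its log-odds run to infinity and its variance term vanishes, so the interval reflects the other arm alone. If that arm is placebo, with 15 patients, the component lost is the one that would normally be larger. The primary interval can then exclude zero without support from the data, and at equal true rates this error runs against ensifentrine.

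The rule also treats the same patients in two ways. Table 5 defines alive and not in respiratory failure as "7-point ordinal scale score is equal to 1, 2, 3, 4 or 5". It defines the invasive ventilation/ECMO endpoint as "The 7-point ordinal scale score is equal to 6", or 7 for an in-hospital death, and SAP 8.5 adds "Patients that die in the study will be handled as worst case in all the analyses". Under those definitions the second endpoint is the complement of the first. A result of 28/30 v 15/15 on the first gets a delta-method interval; the same patients are 2/30 v 0/15 on the second and get none.

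**Working it through.** **Inputs.** From SAP 6.1: n = 30 ensifentrine, 15 placebo. From SAP 8.2: two-sided 5%, so z = 1.96. The plan states no recovery rate, power or interval, so there is no figure to reproduce and the true rates below are assumptions. Differences are ensifentrine minus placebo, in percentage points.

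**Formulas.** With treatment alone in the model, the delta-method standard error is

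SE = sqrt[ pE(1 - pE)/30 + pP(1 - pP)/15 ].

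The Newcombe interval combines the Wilson limits (l, u) of each arm:

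- lower = d - sqrt[(pE - lE)² + (uP - pP)²]
- upper = d + sqrt[(uE - pE)² + (pP - lP)²]

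**Worked case, 26/30 v 15/15.** d = 0.8667 - 1 = -0.1333.

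- Delta: SE = sqrt(0.8667 × 0.1333/30 + 0) = 0.0621; -0.1333 ± 1.96 × 0.0621 gives **-25.5 to -1.2**.
- Newcombe: Wilson limits are 0.7032 to 0.9469 and 0.7961 to 1. Lower = -0.1333 - 0.1635; upper = -0.1333 + sqrt(0.0802² + 0.2039²) = -0.1333 + 0.2191. This gives **-29.7 to +8.6**. Fisher p = 0.285.

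**Other outcomes.**

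| Ensifentrine v placebo | Delta | Newcombe |
|---|---|---|
| 30/30 v 15/15 | 0 to 0 | -11.4 to +20.4 |
| 28/30 v 15/15 | -15.6 to +2.3 | -21.3 to +14.3 |
| 30/30 v 13/15 | -3.9 to +30.5 | -1.5 to +37.9 |

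For 23 to 26 of 30 v 15/15, delta excludes zero while Newcombe includes it (Fisher p 0.077 to 0.285).

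There are 44 outcomes with an arm at 100% and neither at 0. Delta is narrower than Newcombe in 36, including all 30 with placebo at 15/15. It is slightly wider in 8 (30/30 v 4 to 11 of 15): at 30/30 v 10/15 the widths are 47.7 and 46.4 points.

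**The severity term does not cause or cure this.** Fitting the logistic model with the stratum weights (25 iterations):

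- One stratum, 28/30 v 15/15: SE 0.0455, placebo part 0.00000.
- Two strata, 19/20 and 9/10 v 10/10 and 5/5: SE 0.0453, placebo part 0.00000, interval -15.6 to +2.2.
- Two strata, 18/20 and 8/10 v 15/15: -25.4 to -1.3.
- Off the boundary, 27/30 v 13/15: SE 0.1035, placebo part 0.0878.

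**Frequency and coverage.** P(an arm at 100%) = 1 - (1 - pE^30)(1 - pP^15); at 90/90 this is 1 - 0.9576 × 0.7941 = 24.0%. Coverage sums the binomial probabilities over all 31 × 16 outcomes. The rule tested uses Newcombe when an arm is at 0% or 100% and delta otherwise.

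| True rates E/P (%) | P(arm at 100%) | Delta coverage | Coverage with rule |
|---|---|---|---|
| 70/70 | 0.5% | 93.2% | 93.3% |
| 80/70 | 0.6% | 93.2% | 93.2% |
| 90/70 | 4.7% | 92.7% | 92.8% |
| 80/80 | 3.6% | 92.9% | 95.1% |
| 85/85 | 9.4% | 91.5% | 96.6% |
| 90/85 | 12.6% | 89.0% | 96.6% |
| 90/90 | 24.0% | 91.3% | 97.9% |
| 95/90 | 37.6% | 78.6% | 98.2% |
| 95/95 | 57.8% | 96.9% | 99.0% |

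At 95/90, no delta interval with placebo at 15/15 contains the true difference of +5 points. At 95/95, coverage looks adequate partly because the zero-width interval contains the true value of zero.

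**Direction of error at equal true rates** (nominal 2.5% each side):

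| True rate | Wholly below zero: delta | of which an arm at 100% | with rule | Wholly above zero: delta | with rule |
|---|---|---|---|---|---|
| 70% | 4.0% | 0.5 | 3.9% | 2.8% | 2.8% |
| 80% | 5.0% | 3.1 | 2.8% | 2.1% | 2.1% |
| 85% | 6.6% | 5.9 | 1.3% | 1.9% | 2.1% |
| 90% | 7.3% | 7.3 | 0.2% | 1.4% | 1.9% |
| 95% | 2.8% | 2.8 | 0.0% | 0.3% | 1.0% |

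**The case against.** **Reading of the rule.** SAP 9.3 does not define an event, and SAP 9.4 describes one as a given level of need or worse, so zero events might be meant to include zero failures. The misleading interval would then never be printed. The text is open to this, but 9.4.2 points the other way, and on this reading a plausible primary result carries no interval at all. The sentence needs changing either way.

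**Weight.** This is an unpowered exploratory pilot, no decision rests on the interval, raw proportions are always shown, and time to recovery has its own log-rank test. The gap does not inflate apparent benefit, as the wholly-above-zero columns show. All of that stands and limits the consequence to reported precision.

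**Likelihood.** The rates are assumed, and the chance of an arm at 100% runs from 0.5% to 57.8% across the scenarios. That also stands.

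**Mirror image.** The ventilation/ECMO endpoint is missing from the 9.4.2 list, although the opening sentence there covers proportion endpoints generally. Table 5 titles it as patients alive, and shell Table 14.2.18 counts score 6 only. It is therefore an exact complement only under the Table 5 definition and SAP 8.5. The inconsistency survives: a placebo arm at 15/15 on scores 1 to 5 is 0/15 on the ventilation endpoint under either definition.

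**Remedy.** Adding 100% to the existing fallback would be simpler, and coverage of the delta intervals still reported would be 93.5% to 99.5% in the nine scenarios. That removes the wrong interval but leaves boundary results with none. Newcombe is one choice among several; Miettinen-Nurminen gives +0.7 to +38.2 at 30/30 v 13/15, excluding zero where Newcombe does not. That is a reason to name the method in advance.

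**Conclusion.** The concern holds. Followed as written, the SAP applies a delta-method interval when an arm is at 100%, although that arm then contributes no variance. The result is too narrow in 36 of the 44 such outcomes with neither arm at 0, most seriously with placebo at 15/15. The zero variance and the interval widths need no assumed rate. How often it matters does: little with placebo near 70%, appreciably at true rates of about 85% to 95%. The mild undercoverage with placebo at 70% is not a boundary problem, and the boundary rule does not cure it. The point is worth correcting, in proportion to an exploratory pilot whose raw proportions are always visible.

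**What to change.** In SAP 9.3 and 9.4.2, replace "If 0 events in any of the groups only raw proportions will be given" with:

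> When either arm has 0% or 100% of its patients meeting the endpoint, report the raw proportions together with the difference in proportions and its Newcombe 95% confidence interval (the stratified version if more than one severity stratum is used).

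The delta-method interval stays for every other outcome. Giving an interval at 0% as well is an improvement rather than the correction of an error (deaths of 0/30 v 1/15 would give -29.8 to +5.9 points); it also makes the complementary endpoints consistent. If the sponsor also wants nominal coverage near 70%, Newcombe for every outcome gives 95.1% to 99.0% across the nine scenarios.

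The cost is one sentence in each of two sections and a few lines of code. Boundary intervals will usually be wider (28/30 v 15/15: 35.6 points instead of 17.9), coverage at high rates will exceed 95%, and boundary and non-boundary results will use different methods.
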